### **8.3 Safety Analysis Set**

The safety analysis set includes all subjects who received at least one dose of DTG+RPV.

### **8.4 Subgroup Analysis**

Specific study groups (see stratification Variable in 11.1.2) will be analyzed.

## **9 Protocol violations and deviations**

Major protocol violations may include, but are not limited to:

- inclusion/exclusion criteria not met

Other protocol violations or deviations may include, but are not limited to:

- Prescription of JULUCA not according to its indication based on the latest SmPC at the time of prescription;

.

## 10 Statistical Methods

### 10.1 Definition of analysis time window

### 10.2 Year 1, 2, and 3 follow-up windows

**Year 1 follow-up window** is defined as 9 to 15 months [275 days; 457 days] after the therapy start. This window applies to all variables incl. patient reported outcomes.

Rule for two or more assessments in the time window:

The closest available assessment to year 1 (365 days) after therapy start while the participant is on treatment and continued on study within the time window.

**Year 2 follow-up window** is defined as 21 to 27 months [640 days; 822 days] after the therapy start. This window applies to all variables incl. patient reported outcomes.

Rule for two or more assessments in the time window:

The closest available assessment to year 2 (730 days) after therapy start while the participant is on treatment and continued on study within the time window.

**Year 3 follow-up window** is defined as 33 to 39 months [1005 days; 1185 days] after the therapy start. This window applies to all variables incl. patient reported outcomes.

Rule for two or more assessments in the time window:

The closest available assessment to year 3 (1095 days) after therapy start while the participant is on treatment and continued on study within the time window.

#### 10.2.1 Time period for incident (serious) adverse drug reactions and serious adverse events

For incident (S)ADRs/SAEs the following time window will be used:

Date of year 3 follow-up visit minus date of therapy start.

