6.5.2 Data collected for adverse events

Main data being collected may include, but is not limited to:

- Study No
- Centre No

- Subject No
- Event No
- Sender
- Send date
- Event type/description
- Start date
- Outcome
- End date
- Severity/Maximum grade
- Action taken with regard to VH product
- Withdrawal from study as a result of an adverse event/adverse reaction
- Causal relationship to VH product
- Criterion for seriousness

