6.5.5 Reporting of AEs and timelines

The study investigator involved is obliged to collect and report from the time of informed consent to study termination, all ADRs and SAEs.

All ADRs and SAEs will be reported to GSK global safety case management ([contact]) in the form of an electronic safety report within 24hrs of documentation via an automated process.

The safety-related information will be processed according to the legal requirements and country specific regulations to the competent authorities. The recording and reporting of safety data is in a pseudo anonymous format.

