### 10.3 Statistical methods

- Missing data:

For descriptive statistics, analyses will be based on valid (or observed) data per parameter (resulting in different sample sizes).

The following data imputations will be performed:

HIVTSQs (10 item version) score: If  $\leq 3$  items in one questionnaire are missing, mean of all other non-missing items of this participant at this visit will be imputed. If  $> 3$  items in one participant at a visit are missing, the whole score of this participant is set to missing

For HIVTSQs individual item analysis no data will be imputed. However, the basis for this analysis will be the set of participants who completed the questionnaire at both time points

No further data imputation is performed.

- The frequency and proportions (based on the non-missing sample size) of observed levels will be reported for categorical measures.
- Continuous variables will be summarized using the following descriptive statistics: n (non-missing sample size), mean, standard deviation, median, selected quantiles (lower quartile (25%), upper quartile (75%)), minimum and maximum.
- All analyses will be performed respective analyses sets and the subgroups specified in 11.1.2

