### 11.3.5 Study discontinuation prior to year 3 follow-up

- Proportion of participants discontinued the JUNGLE study prior to year 3 follow-up visit
- Reasons for study discontinuation (N, %) - incl. listing of 'other' reason
- Participants discontinued due to virologic reasons: LOCF HIV-RNA copies/mL (listing)
- ART regimes after discontinuation of the JUNGLE study (N, %)

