#### 11.3.10 (Serious) adverse drug reactions and serious adverse events from baseline until year 3 follow-up

Incident (serious) adverse drug reactions [(S)ADRs] and severe adverse events [SAEs] of each participant will be presented in listings and as

- Number and frequency of SAEs [normalized to patient years]
- Number and frequency of (S)ADRs [normalized to patient years]

For definition of periods see 10.2.1.

In detail the following parameters will be evaluated:

Include nature of the (S)ADR/SAE (MedDRA System Organ Class and MedDRA Preferred Term), date and time of onset and resolution, intensity, causal relationship with DTG+RPV, seriousness, interruption or withdrawal of DTG+RPV, countermeasure and outcome.

Handling of repeated events in the summary statistics:

- ‘per participant’: Each subject will only be counted once and any repetitions of (S)ADR/SAE will be ignored; the denominator will be the total population size.
- ‘per MedDRA term’: All MedDRA terms will be counted and the repetitions of (S)ADR/SAE will be not ignored; the denominator will be the total MedDRA term number.

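### SAP 10.2.1 defines the SAE/ADR observation period only through the year 3 visit, so participants without one have no defined person-time for the patient-year rates

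*SAP*

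**What the plan says.** SAP 10.2.1 sets the time window for incident (S)ADRs and SAEs as "Date of year 3 follow-up visit minus date of therapy start". SAP 11.3.10 reports SAEs and (S)ADRs per patient-year and sends the reader back with "For definition of periods see 10.2.1". Both rates are secondary endpoints in Protocol 3.4.2 and SAP 11.3.2.

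Under SAP 10.2 the year 3 window "is defined as 33 to 39 months [1005 days; 1185 days] after the therapy start", and the assessment used must be made while the participant is on treatment and on study.

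Other passages point to wider coverage:
- SAP 8.3 defines the safety set as everyone dosed at least once. SAP 8.1 bases all analyses on the mFAS. SAP 11.3.10 does not say which set it uses. Neither set requires a year 3 visit.
- In the per-participant summary of SAP 11.3.10, "any repetitions of (S)ADR/SAE will be ignored; the denominator will be the total population size".
- Protocol 6.5.5 obliges the investigator to "collect and report from the time of informed consent to study termination, all ADRs and SAEs", and Protocol 6.5.2 lists "Withdrawal from study as a result of an adverse event/adverse reaction" among the recorded items.
- SAP 11.3.5 plans to report "Proportion of participants discontinued the JUNGLE study prior to year 3 follow-up visit".

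On missing data, SAP 10.3 says that "analyses will be based on valid (or observed) data per parameter (resulting in different sample sizes", and it allows no imputation beyond the HIVTSQs score.

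**The concern.** The formula cannot be evaluated without a year 3 visit date. Early leavers have none, and neither do participants still on study whose routine visits miss the window. The plan expects early leavers, since it budgets for dropout and tabulates it, yet no passage gives them an end date such as discontinuation, death or last contact.

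A patient-year rate needs events and person-time from the same people over the same interval. Here the person-time of these participants is undefined and the handling of their events is left open. Those who leave because of a reaction matter for a tolerability summary, and their place in the rates would be decided by whoever programs the table. Two summaries in one section could then rest on different people: percentages on the whole population, rates on those who reached year 3.

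**Working it through.** **The plan's own figure.** SAP 7.2 needs 158 participants at the end and allows 30% dropout: 158 / (1 − 0.30) = 225.7, so 226. This reproduces. So does 158: the exact 95% interval at 90% has width 0.0997 at n = 158 and 0.1001 at n = 157. The plan states no patient-years or event rates, so there is nothing further to reproduce. Only the 30% is used below. It is the planning maximum for study dropout; participants on study with no visit in the window would come on top.

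**How many are concerned.** At the recruitment goal, 0.30 × 250 = 75 participants would have no defined period.

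**Assumptions, not in the documents.** Completers contribute 3 years each; leavers leave at mean time *t*; the leavers' event rate is *k* times that of completers. With dropout fraction *d*, per participant enrolled:
- completer time C = 3(1 − d); leaver time L = d·t
- rate with all observed time and events, relative to completers: (C + kL)/(C + L)
- A, leavers' time and events both dropped: the reported value is 1, so the relative error is (C + L)/(C + kL) − 1
- B, leavers' events kept without their time: the reported value is (C + kL)/C, so the relative error is (C + L)/C − 1, whatever the value of *k*

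**Main illustration, d = 0.30 and t = 1.5.** C = 2.10, L = 0.45.
- A, k = 1: 2.55/2.55 − 1 = 0%
- A, k = 2: 2.55/3.00 − 1 = −15.0%
- A, k = 0.5: 2.55/2.325 − 1 = +9.7%
- B: 2.55/2.10 − 1 = +21.4%

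**The same in absolute terms.** With N = 250, 175 completers give 525 patient-years and 75 leavers give 112.5, which is 112.5/637.5 = 17.6% of the total. Assume 5 events per 100 patient-years in completers (26.25 events) and double that in leavers (11.25 events). All observed data: 37.5/637.5 = 5.88 per 100 patient-years. Reading A: 26.25/525 = 5.00. Reading B: 37.5/525 = 7.14.

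**Range over the assumptions.**

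| d | t (years) | C | L | A, k = 2 | B |
|---|---|---|---|---|---|
| 0.30 | 0.5 | 2.10 | 0.15 | −6.3% | +7.1% |
| 0.30 | 1.5 | 2.10 | 0.45 | −15.0% | +21.4% |
| 0.30 | 2.0 | 2.10 | 0.60 | −18.2% | +28.6% |
| 0.10 | 1.5 | 2.70 | 0.15 | −5.0% | +5.6% |

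**Reach within SAP 11.3.10.** The reference to 10.2.1 stands before the per-participant and per-term summaries and is not confined to the rates. If the window is also used to select events, leavers' events fall in no window, and the per-participant counts and listings lose them too.

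**The case against.** The best defence is that 10.2.1 is meant as an outer bound, matching the span from baseline to year 3 in the heading of 11.3.10, with patient-years meaning each participant's observed time. The surrounding text supports this: the safety set is everyone dosed, 11.3.10 presents the events of each participant, and its percentage denominator is the whole population. This is probably what the sponsor intends. It is not what the formula says. The formula returns no value for a leaver, and nothing else supplies one. A stated rule that fails for a foreseen group goes beyond a detail left to programming.

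A second objection concerns SAP 10.3. A reader might combine it with 10.2.1 and conclude that the plan orders leavers out of numerator and denominator, so that the rates will be understated. The documents do not support that. A leaver's recorded event is observed data, and 10.3 does not say to discard it because a later visit date is missing. Keeping the events would push the rate upward instead. This objection stands: the direction is open.

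Third, the study is descriptive and single-arm. Its tolerability objective is worded in terms of discontinuation due to ADRs and the overall number of SAEs, and reasons for discontinuation are tabulated under 11.3.5. This also stands, and it limits the consequence. It does not remove it, because the rates are themselves listed endpoints.

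**Conclusion.** The point holds and should be fixed. As written, participants without a year 3 visit contribute no defined person-time to the SAE and (S)ADR rates. The rates then either describe completers only, and are biased unless leavers have the same event rate, or are overstated because events are counted without the matching time.

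The size cannot be derived from the documents. At the planned maximum of 30% dropout, with an assumed mean exit at 1.5 years, it runs from 0% (equal rates) to about 15% understatement (doubled rate in leavers) or about 21% overstatement (all events over completer time). Only the 30% is the plan's own number.

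The main effect is on the patient-year rates. A reader might infer that listings and per-participant percentages are certainly safe. That is not assured, since 11.3.10 applies 10.2.1 to the whole section. Nor do the documents show that the tolerability objective as a whole fails, because discontinuations and their reasons are reported separately.

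**What to change.** Replace SAP 10.2.1 with wording such as:

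> For every participant in the safety analysis set, the period runs from therapy start to the year 3 follow-up visit or, if there is none, to the date of study discontinuation or death; if neither is recorded, to the last documented visit or other contact not prompted by an adverse event; capped at day 1185. Events and person-time are counted over this same period, end date included.

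Excluding contacts prompted by an event keeps the length of follow-up from depending on the outcome. Including the end date keeps a fatal event, or one leading to discontinuation that day, in the count.

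In addition:
- Define which date counts as the year 3 visit. SAP 10.2 picks the closest assessment, which can differ between variables.
- Name the analysis set in SAP 11.3.10.
- Report total patient-years beside each rate.

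The cost is a few SAP sentences and one derived variable; SAP 7.4 shows that the discontinuation date is already collected. There are two downsides. Some off-treatment time may be included if treatment stops before study discontinuation, and events reported after the last contact would appear only in the listings.

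Whether HIV-RNA measurements per participant-year (SAP 11.3.2) use the same period is a separate clarification, because 10.2.1 covers only (S)ADRs and SAEs.

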### 10.3 Statistical methods

- Missing data:

For descriptive statistics, analyses will be based on valid (or observed) data per parameter (resulting in different sample sizes).

The following data imputations will be performed:

HIVTSQs (10 item version) score: If  $\leq 3$  items in one questionnaire are missing, mean of all other non-missing items of this participant at this visit will be imputed. If  $> 3$  items in one participant at a visit are missing, the whole score of this participant is set to missing

For HIVTSQs individual item analysis no data will be imputed. However, the basis for this analysis will be the set of participants who completed the questionnaire at both time points

No further data imputation is performed.

- The frequency and proportions (based on the non-missing sample size) of observed levels will be reported for categorical measures.
- Continuous variables will be summarized using the following descriptive statistics: n (non-missing sample size), mean, standard deviation, median, selected quantiles (lower quartile (25%), upper quartile (75%)), minimum and maximum.
- All analyses will be performed respective analyses sets and the subgroups specified in 11.1.2

## 10.4 Participant disposition/analyses sets

Results based on the analyses according to the SAP will be provided in tables and listings and implemented in the study report where appropriate.

Subject disposition will include:

- number of subjects in the FAS, number of subjects in the mFAS
- number of study sites in the FAS, number of study sites in the mFAS
- number and listing of all subjects excluded from the mFAS (with reasons)
- listing of all protocol violations and deviations, including the assessment major/minor and the procedure/consequence which followed.

The following dates will be displayed:

- date of first participant enrolled
- date of last participant enrolled
- date of first start with DTG+RPV
- date of last start with DTG+RPV
- date of last participant last visit

# 11 Planned Analyses

The CSR is planned to comprise the baseline characteristics, all primary and secondary endpoints (see chapters 11.3 and 11.3.2 respectively) as well as other relevant variables as described below.

## 11.1 Variables of interest

### 11.1.1 Variables identified for analysis

#### Baseline characteristics

- Demographics (see 11.2.1)
- Body weight and BMI (see 11.2.2)
- HIV-related characteristics (see )
- Previous ART regime and reason for switch to DTG+RPV (see 11.2.4)
- Laboratory parameters (renal parameters, transaminases, lipids and white and red blood counts) (see 11.2.5)

- Comorbidities and comedication at baseline (see 11.2.6)
- HIV Symptoms Distress Module (SDM) and treatment satisfaction questionnaire (HIVTSQs) (see 11.2.7)

#### Follow-up data

- Virologic response at years 1, 2 and 3\* (including primary and secondary endpoints; for details see 11.3.1 and 11.3.2)
- Immunologic response (see 11.3.3)
- Participant self-assessment of adherence (see 11.3.4)
- Premature study discontinuation: yes/no, reason and date (see 11.3.5)
- Incident comorbidities (see 11.3.6)
- New comediations (see 11.3.6)
- Referrals to another medical specialist (see 11.3.7)
- Laboratory parameters (renal parameters, transaminases, lipids and blood count) (see 11.3.8)
- Body weight and BMI (see 11.3.9)
- (Serious) adverse drug reactions and serious adverse events (see 11.3.10)
- Pregnancies (see 11.3.11)
- HIV Symptoms Distress Module (SDM) and treatment satisfaction questionnaire (HIVTSQs) (see 11.3.12)

*(Variables identified with \* refer to the primary endpoint)*

#### **11.1.2 Stratification variables**

Primary endpoint described under 11.3.1 is planned to be analyzed in respect to the total study population and in following subgroups:

- Age groups (<50 vs ≥50 years)

Secondary endpoints (HIV SDM, HIV TSQs, reason for switch to DTG+RPV, lipids, and safety parameters), described under 11.3.2 are planned to be analyzed in respect to the total study population and in following subgroups:

- Age groups (<50 vs ≥50 years)
- Relevant comorbidities at baseline (yes/no)

## 11.2 Baseline (BL) characteristics

### 11.2.1 Demographics

- Age at baseline [years]
- Proportion of participants aged <50 vs ≥50 years (calculated)
- Sex/gender

### 11.2.2 BL body weight and BMI

- Weight [kg]
- BMI [kg/m^2] (calculated)

### 11.2.3 HIV-related characteristics

- Proportion of participants with CDC stage A or B or C
- Proportion of participants with HIV-RNA <50 copies/mL
- Absolute CD4 cell count [cells/µL]
- Proportion of participants with absolute CD4 cell counts <200/µL; 200-349/µL; 350-499/µL; ≥ 500/µL (calculated)
- Relative CD4 cell count [%]
- Absolute CD8 cell count [cells/µL]
- Relative CD8 cell count [%]
- CD4/CD8 ratio (calculated)
- Proportion of participants with CD4/CD8 ratio <1 vs ≥1 (calculated)
- Detected resistance mutations prior to treatment with DTG+RPV (listing of mutations)

### 11.2.4 Previous ART regime and reason for switch to DTG+RPV

- Time since first HIV diagnosis [years]
- Time on antiretroviral treatment prior switch to DTG+RPV [years]
- Time on last ART regime prior switch to DTG+RPV [years]
- Number of treatment switches (categories), (N, %)
- Last ART regime prior switch to DTG+RPV (N, %)
- Primary and secondary reasons for therapy switch: Proportion of participants switched for the specific reasons; incl. listing of 'other' reason
- Proportion of participants with relevant adverse events of the previous ART treatment; incl. listing of the relevant adverse events

### 11.2.5 Laboratory parameters at BL

#### 11.2.5.1 Renal parameters at BL

- Serum creatinine [mg/dL]
- eGFR [mL/min/1.73 m^2] (calculated)

#### CKD-EPI Creatinine Equation (2021)

$$\text{eGFR}_{\text{cr}} = 142 \times \min(S_{\text{cr}}/\kappa, 1)^\alpha \times \max(S_{\text{cr}}/\kappa, 1)^{-1.200} \times 0.9938^{\text{Age}} \times 1.012 \text{ [if female]}$$

(Scr = standardized serum creatinine in mg/dL;  $\kappa$  = 0.7 (females) or 0.9 (males);  $\alpha$  = -0.241 (female) or -0.302 (male); min(Scr/ $\kappa$ , 1) is the minimum of Scr/ $\kappa$  or 1.0; max(Scr/ $\kappa$ , 1) is the maximum of Scr/ $\kappa$  or 1.0; Age (years))

- Blood nitrogen urea [mg/dL]

#### 11.2.5.2 Liver parameters at BL

- ALT [U/L]
- AST [U/L]
- Gamma-GT [U/L]
- Total bilirubin [mg/dL]
- Bilirubin, direct [mg/dL]
- Alkaline phosphatase [U/L]

#### 11.2.5.3 Lipids at BL

- Total cholesterol [mg/dL]
- LDL cholesterol [mg/dL]
- HDL cholesterol [mg/dL]
- Triglycerides [mg/dL]

#### 11.2.5.4 Blood count at BL

- Hemoglobin [g/dL]
- Hematocrit [%]
- Red blood cells (RBC, erythrocytes) [ $\times 10^6/\mu\text{L}$  (T/L)]
- White blood cells (WBC, leukocytes) [ $\times 10^3/\mu\text{L}$  (G/L)]
- Lymphocytes [%]
- Platelets [G/L]

#### 11.2.5.5 Serum chemistry at BL

- Amylase [U/L]
- Lipase [U/L]
- Lactate dehydrogenase (LDH) [U/L]
- Creatinine kinase (CK) [U/L]
- Serum glucose [mg/dL]
- Uric acid [mg/dL]
- Serum albumin [mg/dL]
- C reactive protein (CRP) [mg/dL]
- Quick [%]

#### 11.2.5.6 Urine chemistry at BL

- Qualitative urine analysis (urine dipstick): leukocytes, pH value, proteins, bilirubin, urobilinogen, nitrite, glucose, ketones, and blood
- Quantitative urine parameters will be listed:
  - Total protein [mg/L]

- Albumin [mg/L]
- Creatinine [g/L]
- Phosphate [g/L]
- Glucose [mg/L]
- $\alpha$ -1-microglobuline [mg/L]

### 11.2.6 Comorbidities, concomitant medication

- Proportion of participants with a diagnosis of the relevant comorbidity-classes (prevalent at baseline)
- Proportion of participants treated with the relevant comedication-classes (prevalent at baseline)

### 11.2.7 HIV Symptoms Distress Module (SDM) and HIV Treatment Satisfaction Questionnaire (HIVTSQs) at BL

#### 11.2.7.1 HIV Symptoms Distress Module (SDM) at BL

The HIV SDM is a 20-item self-reported measure that addresses the presence and perceived distress linked to symptoms commonly associated with HIV or its treatment. HIV SDM is a validated instrument to assess a total of 20 symptoms on a 5-point scale (0: CCI [REDACTED] .'; 1: CCI [REDACTED] .'; 2: CCI [REDACTED] .'; 3: CCI [REDACTED] .'; 4: CCI [REDACTED] .')

Total symptom distress will be calculated as the unweighted sum of the 20 items with scores ranging from 0 to 80. Higher scores indicate higher degrees of symptom distress.

Each of the following parameters of the SDM will be calculated as observed.

- SDM completed (yes/no)
- SDM total score

#### 11.2.7.2 HIV Treatment Satisfaction Questionnaire (HIVTSQs) at BL

The HIVTSQs is a self-reported scale that measures overall satisfaction with treatment and by specific domains e.g., convenience, flexibility. HIVTSQs is a validated 10-item instrument with scores per item ranging from 0 CCI [REDACTED] to 6 CCI [REDACTED] with a recall period encompassing 'the past few weeks'; scores (per item) from 1 to 5 do not have specific descriptions defined on the questionnaire but represent intermediary responses between CCI [REDACTED] (0) and CCI [REDACTED] (6).

HIVTSQs Overall Treatment Satisfaction score:

- will be calculated as the unweighted sum of all 10 items of the HIVTSQs
- Total score range: 0–60 (with higher scores indicating greater treatment satisfaction)

The HIVTSQs total score will be calculated as described in section 10.3 and individual item scores will be calculated as observed.

- HIVTSQs completed (yes/no)
- HIVTSQs total score
- HIVTSQs individual item scores

